4.7.4 Dose Modifications

Dose Modifications

Dose Level	Vosaroxin	Decitabine
	D1 & D4	
-3	50 mg/m ²	20 mg/m ² (Days 1 - 3)
-2	50 mg/m ²	20 mg/m ² (Days 1 -4)

-1	50 mg/m ²	20 mg/m ² (Days 1-5)
0	70mg/m ²	20 mg/m ² (Days 1-5)

4.7.5 Supportive Care:

Supportive care measures including blood products, infection prophylaxis and growth factors will be administered according to institutional and Leukemia Department guidelines.

4.7.6 Concomitant Medications:

Concomitant medications are recommended as prophylaxis for nausea, vomiting, and infections, and are allowed for managing myelosuppression as shown in Table 6. Myelosuppression is expected in patients with AML due to underlying disease, as well as due to chemotherapy (such as vosaroxin and decitabine), or both. Most patients have neutropenia, thrombocytopenia, or both at study entry. Myelosuppression may be managed with growth factor support and blood transfusion according to institutional standard of care, American Society of Clinical Oncology (ASCO) Practice Guidelines, and NCCN Practice Guidelines.

Infections secondary to myelosuppression are common in patients with AML, and may be related to underlying disease, chemotherapy, or both. Therefore, the use of prophylactic antibiotics, antifungal agents, and antiviral agents is recommended. A suggested regimen is ciprofloxacin (500 mg po q 12h), fluconazole (200 mg po qd), and acyclovir (800 mg po q 12h). One dose of prophylactic intrathecal chemotherapy will be allowed with diagnostic lumbar puncture.

All ongoing medications and therapies (including herbal products, nutritional supplements, and nontraditional medications) at screening will be considered prior medications. Concomitant medication data will not be collected or entered into the case report form; however, the subject's medication record will contain a list of concomitant medications. Patients will discontinue study treatment if they intentionally receive or require treatment with a medication prohibited by the protocol. If however prohibited medication is inadvertently administered/ taken by the patient, the patient may remain on study as long as the prohibited medication is discontinued as soon as feasible. End-of-treatment procedures will be performed, and follow-up will commence. Prohibited medications are shown in Table 6.

Table 6: Instructions for the use of concomitant medications and therapies

Category of Use	Medication	Comment on Use	Restriction on Use
Recommended	Prophylactic antibiotics, antifungal agents, and antiviral agents	Strongly encouraged	None
	Antiemetic agents	According to standard of care at MDACC	None
Allowed	Oral allopurinol or rasburicase	At investigators discretion	None
	Intrathecal chemotherapy	At investigators discretion	One dose of low-dose cytarabine or methotrexate with diagnostic LP
	Leukapheresis	According to standard of care at MDACC	Before induction 1 day 1 only
	Red blood cell transfusion	None	None
	Platelet transfusion	None	None
	White blood cell transfusion	At investigators discretion according to standard of care at MDACC	None
	Myeloid growth factors	At investigators discretion according to standard of care at MDACC	None
	Erythropoetin or darbepoetin	At investigators discretion	None
Any other medication for supportive care	At investigators discretion according to standard of care at MDACC	None	
Prohibited	Hydroxyurea	Hydroxyurea at a dose \leq 1.5 g orally daily for up to 10 days is allowed in the first induction course for WBC $>30.0 \times 10^9/L$.	Hydroxyurea cannot be used beyond day 10 of induction 1

MDACC = MD Anderson Cancer Center

5.0 PRETREATMENT EVALUATION:

History and physical exam including measurement of height, weight, and vital signs (blood pressure, heart rate, temperature, and breathing rate) and performance status, CBC with differential and platelets, chemistry profile (total bilirubin, serum creatinine, SGPT or SOOT, uric acid, LDH, potassium, magnesium, glucose), and ECG within 14 days of therapy initiation.

ECHO or MUGA within 28 days prior to treatment start.

Women of childbearing potential must have a negative serum or urine pregnancy test within 3 days before receiving the first dose of study drug.

Bone marrow aspirate and/or biopsy within 28 days of therapy start. The bone marrow evaluation will include immunophenotyping by flow cytometry and cytogenetic studies.

6.1 EVALUATIONS:

6.2 Evaluations During Study:

Patient will have physical examination prior to each course. CBC with differential and platelet counts at least once a week until remission (CR/CRp/CRi), then every 1 to 2 weeks during active treatment, and every 4 to 8 weeks thereafter as long as on study. No differential is needed if the WBC is $< 1.0 \times 10^9/L$. The patients in CR who are deemed eligible to continue on decitabine only will need to have physical examination after every 2-3 courses of decitabine.

Chemistry profile at least weekly until remission, then every 2 to 4 weeks during active treatment.

For those patients who are receiving Decitabine alone without Vosaroxin, as outlined in section 4.6, these patients may receive Decitabine with a local physician but will be required to return to MDACC every two to three cycles for a physical exam.

The patient may have the laboratory work done at a local clinic and the results reported to the research nurse for the study. The laboratory work done at the local clinic will be forwarded to the patient's attending physician at MDACC or PI of the study, who will sign off on the labs to verify that the results have been reviewed.

Outside Physician Participation During Treatment

1. MDACC Physician communication with the outside physician is required prior to the patient returning to the local physician .

This will be documented in the patient record

2. A letter to the local physician outlining the patient's participation in a clinical trial will request local physician agreement to supervise the patient's care (Appendix H)

3. Protocol required evaluations outside MDACC will be documented by telephone, fax or e-mail. Fax and/or e-mail will be dated and signed by the MDACC physician, indicating that they have reviewed it.

4. Changes in drug dose and/or schedule must be discussed with and approved by the MDACC physician investigator, or their representative prior to initiation, and will be documented in the patient record.

5. A copy of the informed consent, protocol abstract, treatment schema and evaluation during treatment will be provided to the local physician.

6. Documentation to be provided by the local physician will include drug administration records, progress notes, reports of protocol required laboratory and diagnostic studies and documentation of any hospitalizations.

7. The home physician will be requested to report to the MDACC physician investigator all life threatening events within 24 hours of documented occurrence.

Bone marrow aspirate and/or biopsy starting on day 21 (+/- 7 days) of therapy and then every 4 weeks (+/- 7 days) as required by leukemia evolution until confirmation of remission (CR/CRp/CRi) or nonresponse. Bone marrow evaluations to include immunophenotyping by flow cytometry and cytogenetics at the discretion of the treating physician.

Bone marrow tests can be ordered more frequently if mandated by development of peripheral blood counts. No repeat bone marrow is necessary if nonresponse or progressive disease can be unequivocally diagnosed from peripheral blood tests or, in patients with a WBC < 0.3 if the bone marrow test is considered noncontributory by the investigator at any time point. Patient will be followed for survival at MD Anderson Cancer Center (MDACC) every 3 to 6 months for up to 5 years after completion of active treatment and while still on study. If the patient is unable to return to MDACC the follow-up visits may be conducted via telephone.

Concomitant medication data will not be collected or entered into the case report form; however, the subject's medication record will contain a list of concomitant medications.

Data regarding adverse events will be collected during the study. Please see **Appendix E** regarding data capturing of adverse events and adverse events source documentation. Protocol specific data will be entered into PDMS/CORe. PDMS/CORe will be used as the electronic case report form for this protocol. Only unexpected AEs will be recorded in the Case Report Form (CRF). The Principal Investigator will sign and date the AE log per each patient at the completion of each course. Following signature, the AE log will be used as source documentation for the adverse events for attribution.

Treatment may be discontinued for a variety of reasons, including patient withdrawal, investigator decision, and reasons specified by the protocol. Reasons for discontinuation of treatments are described below .

6.2 Follow-up Evaluations:

After completion of induction and consolidation treatment patients will continue to be followed at MDACC for 5 years.

Every 4-8 weeks, blood will be drawn for routine standard of care tests. If the patient cannot return to the MDACC clinic for blood draws, the blood draws can be set up at a local clinic closer to the patient's residence and the results reported to the research nurse for the study. The laboratory work done at the local clinic will be forwarded to the patient's attending physician at MDACC or PI of the study, who will sign off on the labs to verify that the results have been reviewed

Every 3-6 months, patients will be scheduled for clinic visits for clinical evaluation and physical examinations. If the patient cannot make it to the MDACC clinic for these visits, the patient can be followed by a local physician. The local physician will perform the physical examination and the records will be forwarded to MDACC.

7.1 DISCONTINUATION OF TREATMENT :

7.2 Discontinuation Criteria for Individual Patients

7.2.1 Patient Withdrawal

Patients may voluntarily withdraw consent to participate in the clinical study at any time and without giving any reason. Their withdrawal will not jeopardize their relationship with their healthcare providers or affect their future care. Patients may also choose to withdraw from study treatment, but agree to remain in the study for follow-up procedures.

7.2.2 Investigator Discontinuation of Patient

The investigator may exercise medical judgment to discontinue study treatment if clinically significant changes in clinical status or laboratory values are noted.

7.2.3 Criteria for Protocol-Defined Required Discontinuation of Treatment

The protocol requires discontinuation of study treatment for the following reasons:

1. Patient requests discontinuation.
2. There is unacceptable toxicity (i.e., NCI CTCAE version 4.0 clinically significant grade 4 drug-related non hematologic toxicity).
3. Patient experiences an NCI CTCAE version 4.0 \geq grade 3 drug-related non-hematologic toxicity or clinically significant infection of any grade that is not recovered by Day 75 from the onset of the toxicity.
4. Patient experiences a third occurrence of an NCI CTCAE version 4.0 clinically significant grade 3 drug related non-hematologic toxicity.
5. Patient experiences study drug related asymptomatic grade 2 total bilirubin or creatinine abnormality that is not recovered by Day 75 from the onset of the toxicity.
6. There is a need for any treatment not allowed by the protocol.
7. Treatment failure or disease relapses. Patients may continue if they are determined to have clinical benefit following discussion with the PI and the treating Physician. The discussion will be documented in the medical record.
8. Investigator discretion.

7.2.4 Follow-Up at Treatment Discontinuation or Early Withdrawal

Patients who discontinue treatment for any reason will complete end-of-treatment procedures. End of treatment procedures will include a CBC with differential and platelets and a limited chemistry profile (total bilirubin, serum creatinine, SGPT or SGOT, potassium, magnesium, glucose). A bone marrow aspiration may be recommended only if non-response or progressive disease cannot be unequivocally diagnosed from peripheral blood. Although treatment will be discontinued at that time, all patients who do not withdraw consent for follow-up, die, or become lost to follow-up, will remain on study for follow-up evaluations. Subject will be followed for toxicity for at least 30 days after the last protocol treatment. The 30 day follow-up visit will be scheduled as a clinic visits for clinical evaluation and physical examinations. If the patient cannot make it to the MDACC clinic for this visit, the required follow up treatment procedure may be done with a local physician and the records forwarded to MDACC. The research nurse will contact the patient by telephone and get a verbal assessment of the patient's condition. The phone conversation will then be documented in the patients charts.

7.2 Study Stopping Rules

The principal investigator and MDACC IND office have the right to terminate this clinical study at any time. The principal investigator and MDACC IND office, as appropriate, will be involved in any decisions regarding terminating the study, temporarily suspending enrollment, or stopping ongoing treatment with study treatment.

Reasons for terminating the clinical study or a study site's participation include, but are not limited to, the following:

- The incidence or severity of an adverse reaction related to treatment in this study or other studies indicates a potential health hazard to patients
- Patient enrollment is unsatisfactory
- Data recording is inaccurate or incomplete
- Study site personnel are noncompliant with study procedures

7.3 Protocol Violations and Deviations

Protocol violations are defined as significant departures from protocol-required processes or procedures that affect patient safety or benefit potential, or confound assessments of safety or clinical activity. A protocol deviation is a departure from the protocol that does not meet the above criteria. Protocol violations or deviations may be grouped into the following classes:

- Enrollment criteria
- Study activities (missed evaluations or visits)
- Noncompliance with dose or schedule, including dose calculation, administration, interruption, reduction, or delay; or discontinuation criteria
- Investigational product handling, including storage and accountability
- Informed consent and ethical issues

8.0 CRITERIA FOR RESPONSE

8.1 Complete response (CR)

- Peripheral blood counts:
Neutrophil count 2: $1.0 \times 10^9/L$
Platelet count 2: $100 \times 10^9/L$
- Bone marrow aspirate and biopsy
:S5% blasts
- No extramedullary leukemia

8.2 Complete response without platelet recovery (CRp)

- Response as in CR but platelets $< 100 \times 10^9/L$

8.3 CR with insufficient hematological recovery (platelets or neutrophils) (CRi)

- Response as in CR but platelets $< 100 \times 10^9/L$ or neutrophils $< 1 \times 10^9$

8.4 Overall Response rate (ORR) = CR + CRp + CRi

8.5 Disease-free survival (DFS)

Time from CR, CRp or CRi until the date of first objective documentation of disease-relapse or death.

8.6 Overall survival (OS)

- Time from date of treatment start until date of death due to any cause

9.1 REGULATORY AND REPORTING REQUIREMENTS

Adverse event reporting will be as per the NCI criteria and the MDACC Leukemia Specific Adverse Event Recording and Reporting Guidelines.

The descriptions and grading scales found in the revised NCI Common Terminology Criteria for Adverse Events (CTCAE) most current version will be utilized for adverse event reporting. (<http://ctep.cancer.gov/reporting/ctc.html>)[44]. (Appendix F)

9.2 Expedited Adverse Event Reporting:

Refer to **Appendix E** for Leukemia-Specific Adverse Event Recording and Reporting Guidelines. Protocol specific data will be entered into PDMS/CORE. PDMS/CORE will be used as the electronic case report form for this protocol. Only unexpected AEs will be recorded in the Case Report Form (CRF). The Principal Investigator will sign and date the AE log per each patient at the completion of each course. Following signature, the AE log will be used as source documentation for the adverse events for attribution.

These guidelines serve to bring the Department of Leukemia in compliance with the institutional policy on Reporting of Serious Adverse Events-definition of expected AE- "All clinical protocols should include a list of the expected and anticipated events or hospitalizations relating to the study treatment" and Guideline for Good Clinical Practice 4.11.1 "All serious adverse events (SAEs) should be reported immediately to the sponsor except for those SAEs that the protocol or other document (e.g., Investigator's Brochure) identifies as not needing immediate reporting".

Adverse event is any untoward medical occurrence that may present during treatment with a pharmaceutical product but which does not necessarily have a causal relationship with this treatment.

Adverse drug reaction is a response to a drug which is noxious and unintended and which occurs at doses normally used in man for prophylaxis, diagnosis, or therapy of disease or for the modification of physiologic function.

Assessing causal connections between agents and disease is fundamental to the understanding of adverse drug reactions. In general, a drug may be considered a contributory cause of an adverse event if, had the drug not been administered, 1) the event would not have happened at all, 2) the event would have occurred later than it actually did, or 3) the event would have been less severe.

Adverse Events (AEs) will be evaluated according to current CTCAE version in each protocol. Only unexpected AEs will be recorded in the Case Report Form (CRF).

Adverse events which are moderate to severe in intensity and which are assessed as possibly or probably related to study drug, may result in the termination of study treatment in the affected study patient. Such termination should be reviewed with the principal investigator at the earliest possible time. Following review with the principal investigator, the study patient may be permanently withdrawn from the study depending upon the nature and severity of the event.

Expected events during leukemia therapy are:

1. Myelosuppression related events (due to disease or leukemia therapy):

a. febrile or infection episodes not requiring management in the intensive care unit

b. epistaxis or bleeding except for catastrophic CNS or pulmonary hemorrhage

c. anemia, neutropenia, lymphopenia, thrombocytopenia, leukopenia, leukocytosis

2. Disease related events:

a. symptoms associated with anemia

i. fatigue

ii. weakness

iii. shortness of breath

b. electrolyte abnormalities (sodium, potassium, bicarbonate, CO₂, magnesium)

c. chemistry abnormalities (LDH, phosphorus, calcium, BUN, protein, albumin, uric acid, alkaline phosphatase, glucose)

d. coagulation abnormalities

e. disease specific therapy (induction, maintenance, salvage, or stem cell therapy)

f. alopecia

g. bone, joint, or muscle pain

h. liver function test abnormalities associated with infection or disease progression

i. disease progression

3. General therapy related events:

a. catheter related events

b. renal failure related to tumor lysis syndrome or antibiotic/antifungal therapy

c. rash related to antibiotic use

4. Hospitalization for the management of any of the above expected events

Abnormal hematologic values will not be recorded on the CRF. For abnormal chemical values grade 3 or 4, the apogee will be reported per course in the CRF.

9.3 Serious Adverse Event Reporting:

An adverse event or suspected adverse reaction is considered "serious" if, in the view of either the investigator or the sponsor, it results in any of the following outcomes:

- Death
- A life-threatening adverse drug experience- any adverse experience that places the patient, in the view of the initial reporter, at immediate risk of death from the adverse experience as it occurred. It does not include an adverse experience that, had it occurred in a more severe form, might have caused death.
- Inpatient hospitalization or prolongation of existing hospitalization
- A persistent or significant incapacity or substantial disruption of the ability to conduct normal life functions.
- A congenital anomaly/birth defect.

Important medical events that may not result in death, be life-threatening, or require hospitalization may be considered a serious adverse drug experience when, based upon appropriate medical judgment, they may jeopardize the patient or subject and may require medical or surgical intervention to prevent one of the outcomes listed in this definition. Examples of such medical events include allergic bronchospasm requiring intensive treatment in an emergency room or at home, blood dyscrasias or convulsions that do not result in inpatient hospitalization, or the development of drug dependency or drug abuse (21 CFR 312.32).

- Important medical events as defined above may also be considered serious adverse events. Any important medical event can and should be reported as an SAE if deemed appropriate by the Principal Investigator or the IND Sponsor, IND Office.
- All events occurring during the conduct of a protocol and meeting the definition of a SAE must be reported to the IRB in accordance with the timeframes and procedures outlined in "University of Texas M. D. Anderson Cancer Center Institutional Review Board Policy for Investigators on Reporting Unanticipated Adverse Events for Drugs and Devices". Unless stated otherwise in the protocol, all SAEs, expected or unexpected, must be reported to the IND Office, regardless of attribution (within 5 working days of knowledge of the event).
- All life-threatening or fatal events, that are unexpected, and related to the study drug, must have a written report submitted within 24 hours (next working day) of knowledge of the event to the Safety Project Manager in the IND Office.

Unless otherwise noted, the electronic SAE application (eSAE) will be utilized for safety reporting to the IND Office and MDACC IRB.

- Serious adverse events will be captured from the time of the first protocol-specific intervention, until 30 days after the last dose of drug unless the participant withdraws consent. Serious adverse events must be followed until clinical recovery is complete and laboratory tests have returned to baseline, progression of the event has stabilized, or there has been acceptable resolution of the event.
- Additionally, any serious adverse events that occur after the 30 day time period that are related to the study treatment must be reported to the IND Office. This may include the development of a secondary malignancy.

(Please see Appendix E regarding data capturing of adverse events and adverse events source documentation.)

9.4 Serious Adverse Event Reporting to FDA :

- Serious adverse events will be forwarded to FDA by the IND Sponsor (Safety Project Manager IND Office) according to 21 CFR 312.32.

It is the responsibility of the PI and the research team to ensure serious adverse events are reported according to the Code of Federal Regulations, Good Clinical Practices, the protocol guidelines, the sponsor's guidelines, and Institutional Review Board policy.

9.4 Serious Adverse event Reporting to Sunesis Inc.

The assigned research staff will send via fax a courtesy copy of the MD Anderson electronic SAE form within the timeframe specified in the protocol but will not answer sponsor queries associated with these SAEs.

10.1 STATISTICS

10.2 Sample size

This will be a single arm, single center, open label study of the combination of vosaroxin with decitabine as an induction therapy in previously untreated patients with acute myeloid leukemia (AML) or high risk myelodysplastic syndrome (MDS) who are elderly (age \geq 60) and/or unable to tolerate standard therapy. A total of up to 84 patients will be enrolled in the study.

Phase I

A total of up to 24 patients will be accrued into the Phase I part.

Phase II

A total of up to 60 patients (including 6 patients treated at the MTD from the Phase I part) will be recruited for the Phase II part.

The primary efficacy endpoint is overall response rate (ORR). $ORR = CR + CR_p + CR_i$. Responses will be evaluated at the end of the first induction cycle and second induction cycle (if a second induction cycle is needed). With a null hypothesis of 40% historical response rate, a sample size of 60 patients would be required to demonstrate a response rate of 60% for the combination of vosaroxin and decitabine using a one-sample exact binomial test and with a two-sided alpha of 0.05 and a power of 82%.

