Vosaroxin and decitabine have non-overlapping primary molecular mechanisms of action. Vosaroxin targets the topoisomerase II and results in G2/M phase arrest and apoptosis. In contrast to vosaroxin, decitabine inhibits the DNA-methyltransferase activity resulting in hypomethylation and cell cycle arrest at the G1 phase via p21(WAF1) and the G2/M phase via the p38 MAP kinase pathway[43]. The non-confluent safety profile of vosaroxin and decitabine (refer to respective toxicity profiles under section 2.2.3 and 2.3.4) and their unique and non-overlapping anti-leukemic activities make them well suited for frontline combination therapy in elderly patients and/or patients unable to tolerate standard therapy for AML or high-risk MDS.

3.1 STUDY DESIGN AND ELIGIBILITY:

3.2 Study Design:

This will be a single arm, single center, open label study of the combination of vosaroxin with decitabine in previously untreated patients with acute myeloid leukemia or high-risk myelodysplastic syndrome who are elderly (age ≥ 60) and/or unable to tolerate standard therapy. The study will consist of a lead-in phase I portion to determine the safe dose of vosaroxin in combination with decitabine to move into the phase II portion of the study. A total of up to 84 evaluable patients (including up to 24 patients in the run-in phase I and up to 60 patients in the phase II) will be treated on this protocol.

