will be submitted to investigational new drug (IND) office for review. Cohort summaries will also be submitted when going to a lower dose cohort in phase I. Once approved, the Phase II portion of the study will be opened. Up to 60 patients will be treated on the Phase II portion. The primary endpoint of the Phase II study will be efficacy as measured by ORR rate. Early stopping rules will be implemented for excessive toxicity or lack of efficacy. Please refer to statistical section 10.2 for details.

4.2 General Study Treatment Plan:

All chemotherapy infusions will be done at MDACC only. The intent of the study design is for all patients to receive up to 7 courses, including up to two courses of induction therapy and up to five courses of consolidation therapy. Treatment will be continued during the duration of the study unless patients exhibit evidence of treatment failure, disease progression, experience an unacceptable toxicity, or the investigator determines that discontinuation of treatment is in the best interest of the patient. Patients will be treated with study drugs based on a calculation determined from the patient's body surface area (BSA). BSA will be calculated before each cycle and will be based on the patient's height (measured at baseline) and weight (measured each cycle). Dosing of both drugs will be based on actual body weight with no capping of dose based on BSA.

4.3 Induction Therapy in Phase 1:

The first 6 patients on study (first cohort) will receive 1 or 2 induction cycles of therapy according to the following starting schedule: vosaroxin will be administered intravenously as a short infusion over 8 to 10 minutes on days 1 and 4 at a dose of 90 mg/m^2 in the first cycle (induction 1) for a total dose of $180 \text{ mg/m}^2/\text{cycle}$ in combination with decitabine at a dose of 20 mg/m^2 administered as a continuous intravenous infusion over approximately 1 hour given daily for 5 consecutive days (Days 1 to 5). These doses have been given safely in previous studies. If a dose is missed, the patient may take the missed dose if it has been less than 48 hours.

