Following are the rules for the monitoring of toxicities in the Phase II portion of the study. Toxicity will be defined as clinically significant non-hematologic drug related grade 3 or higher adverse events. The probability of toxicity is denoted by PE. We assume PE – beta (0.6, 1.4). Our stopping rule is given by the following probability statement: Probability (PE > 0.30 | data) > 0.975. That is, we will stop the study if, at any time during the study, we determine that there is more than 97.5% chance that the toxicity is more than 30%. This stopping rule will be applied in each cohort. The stopping boundaries for clinically significant toxicities observed during the first cycle, based on these assumptions and monitoring conditions found in table 10. We will apply these stopping boundaries starting from the fifth patient and in cohorts of 5. For example, accrual will cease if 4 patients experience clinically significant toxicities during the first cycle among the first 5 patients treated. The operating characteristics are summarized in table 11.

Table 10. Stopping boundaries for Phase II toxicities

The number of patients evaluated for toxicities	5	10	15	20	25	30	35	40	45	50	55	60
The number of patients with DLTs	4	5-6	7-8	9-10	11-12	13-14	15-16	17-18	19	20-21	22-23	24-25

Table 11. Operating characteristics

True Toxicity Rate	Early Stopping Probability	Sample Size		
		25 th percentile	Median	75 th percentile
0.10	0.008	60	60	60
0.20	0.010	60	60	60
0.30	0.082	60	60	60
0.40	0.474	30	60	60
0.50	0.906	15	25	40

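### Counting the six Phase I MTD patients inside the Phase II 60 gives a maximum of 78 patients, not the stated 84, and blurs who enters the Phase II toxicity count

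*Combined protocol and SAP*

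**What the plan says.** **Sample size.** Section 10.2 gives three ceilings: "A total of up to 84 patients will be enrolled in the study", "A total of up to 24 patients will be accrued into the Phase I part", and for Phase II "A total of up to 60 patients (including 6 patients treated at the MTD from the Phase I part". Section 3.2 breaks the total down as "A total of up to 84 evaluable patients (including up to 24 patients in the run-in phase I and up to 60 patients" in Phase II and mentions no overlap. Section 4.2 (Treatment Plan in Phase I and II) says "Up to 60 patients will be treated on the Phase II portion", again without mention of the six.

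**Phase I gate.** Under section 4.4 a dose level becomes the MTD, and Phase II opens, only if at most 1 of 6 evaluable patients has a first-cycle DLT.

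**Toxicity monitoring.** Section 10.3 introduces the rule with "Following are the rules for the monitoring of toxicities in the Phase II portion of the study". It stops when Pr(PE > 0.30 | data) > 0.975 under a Beta(0.6, 1.4) prior, with looks every 5 patients. Its worked example is that "accrual will cease if 4 patients experience clinically significant toxicities during the first cycle among the first 5 patients treated". Table 10 runs from 5 to 60 patients, and its event row is labelled "The number of patients with DLTs". The six are not mentioned. Table 8, for response futility, uses the same 5-to-60 grid and is equally silent.

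**The concern.** The total and its parts are given in the same section and disagree by six. The disagreement decides whether 54 or 60 new patients are enrolled in Phase II.

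The same parenthesis matters for safety monitoring, because the six are not a random sample of outcomes. They belong to the cohort that let Phase II open, so by construction they carry at most one DLT. Adding such a group to the front of the toxicity count makes the stopping rule harder to trigger. Whoever applies Table 10 needs to know the denominator.

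**Working it through.** **1. Total.** Four dose levels × 6 = 24 in Phase I. Distinct patients = 24 + 60 − 6 = 78. With 1, 2, 3 or 4 Phase I cohorts used, the maximum is 60, 66, 72 or 78. The figure of 84 = 24 + 60 needs either no overlap or six patients counted twice.

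**2. Response power.** The stated 82% reproduces first. With an exact binomial test and upper tail at most 0.025 at 40%, n = 60 needs at least 33 responses (tail 0.0133) and has power 0.822 at 60%. With n = 54, at least 30 responses are needed (tail 0.0149) and power is 0.791. So 82% holds for 60 analysed patients, whether 54 + 6 or 60 new, and becomes 79% if only 54 are analysed.

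**3. Toxicity triggers.** After x events in n patients, PE ~ Beta(0.6 + x, 1.4 + n − x). The smallest x giving Pr(PE > 0.30) > 0.975 is 4, 7, 9, 11, 13, 15, 17, 19, 20, 22, 24 at n = 5, 10, …, 55. Reaching 60 is not an early stop.

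**4. Stopping probability once Phase II is open.** This is an exact recursion over patients, removing the mass at or above the trigger at each look. "Six counted" starts from Bin(6, p) restricted to 0 or 1, with looks at 10 to 55. "54 new" has looks at 5 to 50, and "60 new" at 5 to 55.

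| True toxicity | 30% | 40% | 50% |
|---|---|---|---|
| Table 11 as printed | 0.082 | 0.474 | 0.906 |
| Posterior rule, 60 new | 0.083 | 0.471 | 0.906 |
| Posterior rule, 54 new | 0.080 | 0.445 | 0.884 |
| Posterior rule, six counted | 0.017 | 0.240 | 0.749 |
| Table 10 lower ends, 60 new | 0.277 | 0.740 | 0.976 |
| Table 10 upper ends, 60 new | 0.151 | 0.607 | 0.949 |
| Table 10 lower ends, six counted | 0.087 | 0.484 | 0.903 |

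With 60 new patients the posterior rule matches Table 11 within 0.003 at 20–50% (at 20%, 0.008 against the printed 0.010). It does not match at 10% (0.0005 against 0.008), nor the lower quartile of sample size at 50% (10 against 15).

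**5. End to end.** P(Phase II opens) = P(Bin(6, p) ≤ 1) = 0.420 / 0.233 / 0.109 at 30/40/50%. The probability that the dose is rejected in Phase I or stopped in Phase II is 1 − P(open) × (1 − stop). At 40%:

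- 54 new: 1 − 0.233 × (1 − 0.445) ≈ 0.870
- six counted: 1 − 0.233 × (1 − 0.240) ≈ 0.823

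The gap is 0.027 / 0.048 / 0.015 at 30/40/50%. With Table 10's printed boundaries the gap at 40% is similar: 0.055 (lower ends) and 0.053 (upper ends).

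**6. First look that can stop, six counted.** At n = 10 there are at most 1 + 4 = 5 events. The posterior rule needs 7, so it cannot stop before n = 15, where at most 1 + 9 = 10 are possible and 9 are needed. Table 10 prints 5–6 at n = 10, so its lower end could just be reached.

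**The case against.** Every figure is worded as a ceiling, and 78 satisfies a ceiling of 84. No analysis uses 84. That stands: a reader might infer that the trial would over-enrol, and nothing in the documents supports that. The mismatch remains. Nor are the extra six an allowance for replacements, since section 3.2 describes all 84 as evaluable.

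On toxicity, the text largely answers the question. The rule is for the Phase II portion, sections 3.2, 4.4 and 4.5 speak of subsequent patients, and 4 events in the first 5 essentially cannot happen if the six come first. Against this are only the parenthesis in section 10.2 and Table 10's run to 60 with its row label. So new patients only is the better reading, though it is not stated.

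A reader might also infer that counting the six halves the protection against a toxic dose. The halving is conditional on a 40%-toxic dose having passed Phase I, which has probability 0.233; overall the loss is about 0.05. Counting all patients at the selected dose is also a legitimate Bayesian choice.

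Finally, a reader might take Table 11 as proof of which count was intended. It is not: the posterior rule with 60 new patients and Table 10's lower ends with the six counted both come close to it.

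**Conclusion.** The total is wrong as written: section 10.2's own counting gives at most 78 distinct patients, six fewer than the 84 stated there and in section 3.2. This needs no assumption beyond the text.

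The toxicity count is a secondary ambiguity of modest effect: 0.445 against 0.240 at 40% toxicity once Phase II is open, and 0.870 against 0.823 end to end. These figures use the posterior rule and treat a Phase I DLT as the same event as a Phase II toxicity. The definitions differ somewhat: section 4.4 adds a hematologic DLT and limits the non-hematologic part to grade 3–4 in 28 days, while section 10.3 counts non-hematologic grade 3 or higher in the first cycle.

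Naming the denominator does not settle the monitoring by itself, because Table 10's printed ranges do not give Table 11 with new patients only. With 60 new patients at 40%, the choice of boundary moves the stopping probability from 0.471 to as much as 0.740.

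It would go too far to say that the response test pools two schedules. Sections 3.2 and 4.4 carry the Phase I schedule into Phase II, while section 4.5 requests a changed induction dose and also allows the Phase I MTD. Pooling would mix schedules only if the six had a schedule other than the Phase II one, and the documents do not establish that.

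**What to change.** 1. **Sections 3.2 and 10.2.** Either state the maximum as 78 (24 + 54 new), or delete the parenthesis and keep 84 (24 + 60 new). The first adds no enrolment. The second means up to six more new Phase II patients, within the stated ceiling.
2. **Section 10.3, boundaries.** Whichever count is chosen, first reconcile Table 10 with Pr(PE > 0.30 | data) > 0.975, using the triggers in step 3 of the working.
3. **Section 10.3, denominator.** State that the toxicity rule applies to newly enrolled Phase II patients, and say whether the Table 8 futility looks use the same count. Under the posterior rule Table 11's stopping probabilities at 20–50% can then stay with 60 new patients, and are within 0.03 with 54; the 10% row needs correcting. If the six are to be counted instead, reprint Table 11 conditional on at most 1 DLT in 6 and replace the first-5 example.
4. **Phase II schedule.** Reconcile sections 3.2 and 4.4 with section 4.5. Pool the six in the response test only if they received the Phase II schedule. If only 54 patients are analysed, state the power as 79%.

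The cost is a few sentences and corrected tables. Monitoring new patients only gives up six patients of toxicity information.
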